4.2 OVERALL DESIGN

As shown in Figure 1 (on page 9), the proposed multisite SMART will involve randomization at two stages. At Stage 1, all student participants ($N = 480$) will be randomized to 4-6 weeks of CAMS or TAU. Beginning at session 4, the counselor will rate the student participant in terms of clinical response. Insufficient responders (e.g., non-responders) to Stage 1 will be re-randomized to one of two Stage 2 treatments for an additional 1-8 weeks: 1) CAMS (either continued or for the first time) or 2) CC-DBT.

Thus, four ATSSs are possible:

- ATS-1: Start with CAMS, if responding, enter maintenance treatment; if not, continue with CAMS;
- ATS-2: Start with CAMS, if responding, enter maintenance treatment; if not, switch to CC-DBT;
- ATS-3: Start with TAU, if responding, enter maintenance treatment; if not, switch to CAMS;
- ATS-4: Start with TAU, if responding, enter maintenance treatment; if not, switch to CC-DBT.

Our pilot showed at Stage 1, 48% and 44% treatment response rates across CAMS and TAU, with 27% and 17% attrition rates, respectively—differences not statistically significant. Based on these findings, we assume an equal response rate of 50% across both Stage 1 treatments (CAMS and TAU), leaving $N=240$ participants eligible for Stage 2 treatments. Treatment responders at the end of Stage 1 will end study treatment and enter maintenance, which includes monthly monitoring and continued assessments with the IEs. All student participants will complete weekly measures as part of treatment. Research assessments by independent evaluators (IEs) will be conducted at baseline, mid-Stage 1 (Week 3), end of Stage 1 (Week 6), mid-Stage 2 (Week 10), end of Stage 2 (Week 14), and at 3-month follow-up (Week 26).

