6.3 MEASURES TO MINIMIZE BIAS: RANDOMIZATION AND BLINDING

Randomization

We will rely on an adaptive-biased coin design¹⁰⁹ to attempt to balance conditions at each stage based on gender, previous suicide attempt(s), and current psychotropic medications. At Stage 2, the PC will obtain information on the blocking variables, along with the tailoring variable, from counselors and the electronic medical record (EMR; Titanium for all sites) prior to randomization. The PC at each site will randomize subjects via the centralized database using a customized system tailored for the SMART design housed at the Duke Data Center.

All assessments of the main endpoints will be performed by the independent evaluators (IEs), who will remain blind to treatment status. It is always possible that student participants could tell the IE during their assessments about the type of therapy they have been receiving. To mitigate this risk, all student participants will be reminded about the importance of not telling the IEs which treatment they received. It is also possible that counselor participants could tell the IE which treatment condition a particular student participant is in; counselor participants will be frequently reminded not to do so. To evaluate how well blinding was maintained, the IEs will be asked to indicate what treatment group(s) they thought the student participant belonged to at the end of stage 1 and, if applicable, at the end of stage 2.

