A student participant in Stage 1 showing significant worsening may be re-randomized to Stage 2 conditions earlier. Similarly, students who begin the study with significant suicidality and show no improvement after 4 sessions may also be considered for early randomization to Stage 2.

Primary DV: Suicide-Related Behaviors – Relevant to Aims 1, 2, and 3.

Recognizing that measurement of suicide-related behaviors is fraught with challenges,¹¹² we are defining SR as “suicidal ideation, attitudes, behaviors and plans which take into account severity, intent, and ability to cope with ideation without engaging in suicidal behaviors, such as planning/rehearsal, NSSI, suicide attempts (SAs), and suicide.” Our primary assessment measures for SR are two interviews to measure suicidal ideation (SI; defined as self-reported thoughts of suicide-related behavior) and suicidal behaviors, including suicide attempts and non-suicidal self-injury (NSSI). Suicides will also be tallied.

- 1) The Scale for Suicide Ideation—Current (SSI)^{99,113} is a 19-question interview that assesses the student participant’s highest SI in the past 2 weeks, including attitudes, behaviors, and plans. Each item is rated as 0,1, or 2 with a total scale of 0-38. The IEs will be trained and certified on the SSI.
- 2) The Self-Injurious Thoughts and Behaviors Interview (SITBI)¹¹⁴ is a 3-15-minute interview containing modules that assess SI, suicide plans, suicide gestures, suicide attempts, and NSSI. The SITBI has been used with college students.^{115,116} The IEs will be trained and certified on the SITBI.

Secondary DVs/Covariates: Functioning – Relevant to All Aims

- 1) The CCAPS-34¹⁰⁷ assesses key domains of college student mental health (Depression, Generalized Anxiety, Social Anxiety, Academic Distress, Eating Concerns, Substance Use, and Hostility/Anger) and an overall Distress Index score. Students respond to questions using a 5-point rating scale (“*not at all like me*” to “*extremely like me*”). The CCAPS-34 takes only 2-3 minutes to complete¹⁰⁷ and is widely used in CCCs.²²¹ The CCAPS will be assessed at all assessment points and at every session. The question on SI will screen prospective participants and the weekly administration can track SI fluctuations more frequently.

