Assuming about 50% response (N=240) and about 50% insufficient response rate [N=240, which is chosen to be slightly higher for a value divisible by the four possible treatment paths from Stage 1 to Stage 2 (CAMS-CAMS, CAMS-DBT, TAU-CAMS, and TAU-DBT) (based on pilot data)] to Stage 1 treatments corresponding to N=60 potential student participants to be randomized to each of the 4 Stage 2 arms among the non-responders as illustrated in the Schema Figure in section 1.2. We anticipate an at most Stage 1 attrition rate of about 25% among those with an insufficient response leaving N=180 total student participants to be randomized in Stage 2 (approximately 45 student participants per ATS). Estimates of attrition are chosen as equal across each treatment path but are in essence worst case scenarios, where we may see less attrition for specific treatment paths compared to others; therefore, all power estimates are conservative, with more power achievable with more available student participants for different treatment combinations. Based on the method outlined by Oetting and colleagues¹⁸² and a within-person correlation of 0.60, 2.5% Type-I error, we will have over 80% power to detect a difference of ≥ 3.4 ($d = 0.34$) in change in SSI between DBT vs. CAMS.

Power for Aims 4 and 5:

Best practices for power calculations for mediation and moderation models within SMART designs are still debated. For mediation, we will use the work of Fritz and MacKinnon,¹⁸³ who document sample size requirements to guarantee 80% power under the sequential regression framework¹⁶⁶ and the formulas of Vittinghoff et al.¹⁸⁴ Under the assumption of a medium effect for intervention on the mediator and a medium effect for intervention on outcome covarying

the mediator, and an alpha=0.025, the total sample size is calculated as N=166. Therefore, our design consisting of a sample size of 480 within Stage 1 and at least 90 subjects per two Stage 2 arms (CAMS vs CC-DBT) (N=180 total), is sufficiently powered to detect mediation within Stage 2. For moderation, we use Cohen's¹⁸¹ power tables, our sample size of 480 at the start of Stage 1 and at least 90 subjects per arm at Stage 2 is more than sufficient to detect a medium-to-large ES for a moderator.

Table 8. The 4 Adaptive treatment strategies embedded in the proposed SMART					
Adaptive Treatment Strategy	Stage 1 Treatment	Status at End of Stage 1	Stage 2 Treatment	Cells Involved in Comparisons	

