9.3 CAMPUS TRIAL STATISTICAL ANALYSES

9.3.1 GENERAL APPROACH

Overview and Intent-to-Treat. The proposed trial design of adaptive treatment strategies (ATSSs) is like a factorial design;^{156,157,158,159} different analytic subgroups (see Table 8) are combined to answer different questions. Aim 1 is the trial's primary aim; Aims 2-5 are secondary aims and Aim 6 as an implementation aim. All student participants, once randomized, will be included in the intent-to-treat sample, and every effort will be made to collect all primary and secondary outcomes even if a student participant does not engage in randomly assigned treatments. The primary outcome of interest is suicidal risk, which includes suicidal ideation as well as suicide-related behaviors, such as non-suicidal self-injury (NSSI) and suicide attempts (SAs); however suicidal ideation is the primary DV due to relatively low rates of suicidal behaviors post-baseline with college students. Suicides will be tallied as well. All analyses allow for the inclusion of covariates listed as demographics and covariates in Section 8.1. Covariates will enter the model based in clinical importance (gender, age, current alcohol use, current substance use, etc.) and retained on a case-by-case basis based on statistical significance.

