9.3.2 ANALYSIS OF THE PRIMARY ENDPOINT(S)

Aim 1 analyses (Primary Aim) will compare and contrast the 4 pre-specified ATSSs embedded in the SMART design to determine whether one is clearly better or worse than the others with respect to mean suicidal ideation (SI) and suicide-related behaviors (NSSI and suicide attempts), which are the primary outcomes, at the end of 14 weeks of treatment. The data analysis method of Robins and colleagues^{160,161} will be used to contrast the 4 ATSSs based on reducing

suicide-related risk behaviors (SI, NSSI, and suicide attempts) to determine whether any of the interventions appear to be clearly better or worse than others. As part of the design, a student participant will contribute differentially to one or more of the 4 strategies (depending on the treatments to which he or she is randomized and whether he or she is a treatment responder), requiring a weighted comparison. Specifically, this analysis involves a weighted comparison of the cells A+B vs. A+C vs. D+E vs. D+F (see Table 8); the method by Robins and colleagues^{160,161} weights each student participant using the known randomization probabilities. Linear contrasts among the components of the ATSSs will be performed to further understand impact on efficacy. Similar analyses will compare the 4 strategies on the follow-up and secondary outcomes outlined above. Additionally, in response to reviewers' input, a composite outcome including suicidal ideation, suicide attempts, and NSSI will be derived. Death by suicide will be tallied but not included in the composite score. Song and colleagues¹⁶² provide a thorough discussion of the best ways to create composite scores, especially when dealing with a mixture of continuous and count outcomes. The analysis team will determine the best approach in the formation/derivation of the composite using the steps discussed by Song et al¹⁶². Similar analyses will compare the 4 strategies on the derived composite as outlined above.

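### Aim 1 fixes its weights at the known randomisation probabilities and prespecifies no use of earlier SSI scores; estimating the weights from SSI would be a cheap precision gain, not the repair of an error

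*Combined protocol and SAP*

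**What the plan says.** Section 9.3.2 compares the four adaptive treatment strategies (ATSs) on suicidal ideation and behaviours "at the end of 14 weeks of treatment", by a method that "weights each student participant using the known randomization probabilities". It names no weight model and gives no role in Aim 1 to SSI from baseline, Week 3 or Week 6.

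Section 9.3.1 states: "All analyses allow for the inclusion of covariates listed as demographics and covariates in Section 8.1". Those covariates are to be "retained on a case-by-case basis based on statistical significance". Section 8.1 puts CCAPS, CGI and academic functioning under its covariate heading. SSI appears there as the primary outcome, not as a covariate.

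Section 6.3 uses an adaptive biased coin "to attempt to balance conditions at each stage based on gender, previous suicide attempt(s), and current psychotropic medications". Ideation severity is not a balancing factor.

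Section 4.2 schedules evaluator assessments at baseline and Weeks 3, 6, 10, 14 and 26. Section 4.4 allows early re-randomisation after session 4, so the Week 6 SSI may come after a student's second assignment.

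Section 9.2 uses "a within-person correlation of 0.60, 2.5% Type-I error" for Aim 3 without naming the occasions. For Aim 2 it gives a baseline to Week 26 correlation of up to 0.40, and 0.3 for follow-up.

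**The concern.** Insufficient responders are randomised twice, so under 1:1 allocation they carry weight 4 against 2 for responders, which makes the ATS means noisy. Chance imbalance in SSI at either randomisation adds to that noise, and neither the randomisation nor the Aim 1 analysis is set up to remove it.

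SSI measured during Stage 1 cannot safely be a covariate in the ATS mean model, because it is partly a result of Stage 1 treatment. It can enter the Stage 2 weights, because it precedes the Stage 2 assignment. Assignment is random, so weights estimated from variables measured beforehand remain valid and do not increase large-sample variance.

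At stake is the precision of the primary comparisons, most of all ATS-2 against ATS-1, which differ only in how insufficient responders are treated.

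**Working it through.** **1. The plan's own figure.** Let r be the Stage 1 response rate, with 1:1 allocation at both stages. With known weights, an ATS mean has variance 2[r + 2(1−r)]σ²/N. Two ATSs with the same first stage have covariance 2rσ²/N. Set the best ATS 0.25 SD ahead of the other three (Section 9.2). The probability of selecting it is then:

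- r = 0 (conservative), N = 384: 90.0%. Since 384/0.80 = 480, this matches the stated 90% if 20% loss was assumed (my assumption; the plan gives no Aim 1 dropout).
- N = 480, no loss: 93.3% at r = 0 and 97.5% at r = 0.5.
- N = 360 (25% loss): 88.9% at r = 0 and 94.9% at r = 0.5.

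At the plan's 50% response rate the target is met with known weights.

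**2. Contrast variances with known weights, r = 0.5.** Each mean has variance 2(1.5)σ²/N = 3σ²/N, and the same-start covariance is σ²/N.

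- Same-start contrast: 2(3 − 1)σ²/N = 4σ²/N.
- Different-start contrast: 2 × 3σ²/N = 6σ²/N.

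**3. Large-sample gain from estimated weights.** Let ρ_base and ρ_pre be the correlations of Week 14 SSI with baseline SSI and with the last SSI before re-randomisation. The variance reduction is ρ_pre² for same-start contrasts and (4ρ_base² + 2ρ_pre²)/6 for different-start contrasts.

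- ρ_pre 0.6, ρ_base 0.4: 36%, and (0.64 + 0.72)/6 = 23%.
- ρ_pre 0.4, ρ_base 0.3: 16%, and (0.36 + 0.32)/6 = 11%.

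**4. Simulation at N = 480.** There were 3,000 trials per scenario, with normal SSI, no treatment effect, no missing data and SSI-only weights (Stage 2 on baseline, Week 3 and Week 6 scores by arm). Entries are reductions in contrast variance; a minus sign is a loss.

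| Week 6 / baseline correlation with Week 14 | Same-start vs known | Same-start vs known + baseline SSI | Different-start vs known | Different-start vs known + baseline SSI |
|---|---|---|---|---|
| 0.6 / 0.4 | 36% | 21% | 22% | 5% |
| 0.4 / 0.4 | 19% | 1% | 17% | 0% |
| 0.4 / 0.3 | 16% | 6% | 11% | 1% |
| 0.3 / 0.3 | 12% | 1 to 3% | 10% | −1 to 0% |
| 0 / 0 | −3% | −3% | −1% | −1% |

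Other simulations at 0.6/0.4 give 32-38% and 21-24% against known weights. Correlations of 0.6 at every occasion would give 42% and 37%, but that exceeds any baseline correlation the plan states.

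**5. Closer to this trial.** Response is a counselor rating of improvement in suicidal risk, so insufficient responders will have a restricted SSI range. Section 9.2 also expects up to about 25% attrition among them. With response tied to SSI, 25% attrition and correlations of 0.4/0.3, SSI-only weights gain about 12% same-start and 7-11% different-start.

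**6. A larger weight model.** In the same unfavourable setting, a Stage 2 model fitted by arm that also carries the balancing factors, CGI-I and CCAPS gives about −2% to 4% against known weights. It can be up to 10% worse than baseline-SSI adjustment.

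**The case against.** The strongest reply is that nothing is broken. Known weights are unbiased, and estimated weights would move the selection probability at N = 480 and 50% response only from 97.5% to 98.2-99.0%. That stands, and it is why this is an improvement and not an error.

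A reader might infer that Aim 1 is underpowered. At 0.6/0.4, simulated standard deviations of 0.0892 (ATS-2 vs ATS-1) and 0.1127 (ATS-2 vs ATS-4) give power Φ(0.25/0.0892 − 1.96) = 80% and Φ(0.25/0.1127 − 1.96) = 60%. With estimated weights (0.0717 and 0.0993) these become 94% and 71%. But the plan sizes Aim 1 on selection and sets no pairwise 5% test for it, so these figures show no shortfall against its own criterion.

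A reader might also infer that earlier ideation data are thrown away. They are not: Section 9.3.1 permits covariates, CCAPS (which has an ideation item) is on the list, and the Aim 8 Stage 2 model starts from the time of re-randomisation. What is left is that SSI is not prespecified for Aim 1 and that covariate retention depends on significance.

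Finally, baseline-SSI adjustment alone gives most of the different-start gain, and two of the three Hypothesis 1 comparisons (ATS-2 vs ATS-3 and ATS-4) are different-start. This too stands. The distinctive benefit of estimated weights is for same-start contrasts.

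**Conclusion.** The point holds as a low-cost gain in precision. Against plain known weights, SSI-only estimated weights lower variance by roughly 12-38% (same-start) and 7-24% (different-start). Beyond baseline-SSI adjustment the gain is about 2-25% and about zero to 8%.

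These ranges are assumptions, not plan figures. It is tempting to read the 0.60 for Aim 3 as the Week 6 to Week 14 correlation and quote a single gain of 20-35%. The plan does not say which occasions it means; a same-start gain of 20% needs a correlation of about √0.20 = 0.45, and 35% needs √0.35 = 0.59. Nor is the gain free: an uninformative SSI costs about 1-3% of variance.

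The calculations also assume 1:1 allocation by simple balanced randomisation, not the adaptive biased coin.

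**What to change.** In Section 9.3.2, prespecify estimated weights for Aim 1:

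- Stage 1: a logistic model on baseline SSI.
- Stage 2: among insufficient responders, by Stage 1 arm, a logistic model on baseline SSI and the last SSI obtained before that student's own re-randomisation. Choose this score by actual date, because early re-randomisation and the one-week assessment window can place the Week 6 score after assignment.
- Do not add several weakly predictive variables.
- Use standard errors that account for estimating the weights.
- State a rule for a missing pre-assignment SSI.
- Keep the known-weight analysis as a sensitivity analysis.

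The cost is SAP wording, modest programming and a weight model fixed in advance. No extra participants or assessments are needed.

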9.2 CAMPUS TRIAL SAMPLE SIZE DETERMINATION

Power for Aim 1:

Sample size for the study is based primarily on Aim 1, although we also provide effect size (ES) estimates for the other aims given the proposed sample size. With respect to Aim 1, with a total sample of 480, the approach provided by Crivello and colleagues^{178,179,180} guarantees that the adaptive intervention with the lowest estimated mean suicide risk (ideation + behaviors) at post-treatment is, in fact, the best adaptive intervention with 90% probability. This calculation assumes that the best two ATSSs differ by $d = 0.25$ (or ≥ 2 points on the SSI), which corresponds to a small ES estimate.¹⁸¹

Power for Aim 2:

Aim 2 is a two-sample comparison (cells A+B+C vs. D+E+F). Using a two-side, two-sample t-test based on Type-I error rate of 2.5%, a sample of 240 randomized to each Stage 1 treatment arm (N=480 total), we will have 85% power to detect a small, standardized ES of $d = 0.30$ in the between groups difference in change on the primary outcomes. Based on prior studies and our pilot data with $SD=7$ for SSI,¹¹³ this ES corresponds to a clinically meaningful difference of 2 in the SSI. Note that this is a conservative estimate of power: in the repeated measures LMM, power increases in proportion to the within person correlation in baseline to 26-week SSI which can be as high as 0.40 ($p < .01$, based on pilot data). At 3-month follow-up (assuming a baseline to 48-week within correlation of 0.3) we will have 94% power to detect the same moderate ES.

Power for Aim 3:

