Aim 2 analyses will contrast ATSSs beginning with CAMS vs. interventions beginning with TAU (i.e., to evaluate the main effect of initial treatment) on change (decrease) in suicide-related risk behaviors (SI, NSSI, and suicide attempts—the primary outcomes) from baseline to the end of Stage 2 (the primary contrast). This is a comparison of cells A+B+C vs. D+E+F (see Figure 2 and Table 8). Note that the primary continuous longitudinal outcome is assessed at baseline, mid-Stage 1 (3 weeks), post Stage 1 (6 weeks), mid-Stage 2 (10 weeks), post-Stage 2 (14 weeks) (end of acute treatment) and then again at 3-month follow-up (26 weeks), for a total of 6 measurement occasions. Linear mixed models¹⁶³ (LMM, also known as random effects or growth curve models), fit with SAS PROC MIXED will be used to analyze the longitudinal data. LMMs use all available measurements, allowing student participants to have an unequal number of observations and producing unbiased parameter estimates as long as unobserved values are missing at random. The analysis will fit a LMM with fixed effects for the intercept, time, group, and a group-by-time interaction term, where group is an indicator of phase-one treatment (CAMS vs. TAU as referent). The LMM will also include random effects for the intercept and time and an unstructured within-person correlation structure for the residual errors and will adjust for the following measures collected at baseline (pre-randomization): site, age, race, and clinical severity. Model diagnostics will be used to determine suitability of more parsimonious (e.g., autoregressive) correlation structures, and nonlinear (e.g., quadratic) effects for time. We do not expect the intervention effects to be attenuated due to counselor participants who are cross classified between the interventions. Nonetheless, we will assess the potential attenuation by assessing the counselor x intervention interaction. If significant, we will examine if the attenuation effect is limited to a select few counselors and eliminate as needed to remove potential counselor contamination of intervention effects. Counselor will be treated as a random effect which models potential correlation between student participants within a common counselor. If there is not sufficient variance, indicated by the reliability estimate of the random effect falling below 0.02 (a slighter lower threshold compared to

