Raudenbush and Bryk¹⁶⁴ (p.125), we will treat counselor as a fixed effect. The primary contrast is between groups' difference in change from baseline to month 6 (end of acute treatment through Stage 1 and Stage 2 active treatment). The follow-up contrast at week 26 (12 weeks post-acute treatment) will also be examined in this and in all subsequent analyses. LMMs like the above for the primary outcome will be run for the secondary longitudinal outcomes: CAMS vs. TAU on CCAPS subscales (Depression, Anxiety, Academic Distress, Overall Distress), CGI-I and CGI-S (measured by IE), and cumulative GPA.

AIM 3 analyses will examine the relative effectiveness of switching to a more comprehensive suicide-focused treatment approach (e.g., CC-DBT) among those who do not respond sufficiently to Stage 1 treatments vs. a less intensive suicide-focused approach (e.g., CAMS). This analysis is a comparison of cells C+F (switch to CC-DBT) vs. B+E (switch or continue with CAMS) in Table 8. Both primary and secondary longitudinal outcomes outlined above will be examined using an LMM like that described above, but (a) including only the subset of responders to Phase 1 treatment, (b) defining group as switching to CC-DBT (cells C+F) vs. continuing or switching to CAMS (cells B+E), and (c) using monthly longitudinal outcomes from week 4 to week 24 (7 measurement occasions).

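### NSSI and suicide attempts have no count or binary model; the only model given for Aims 2, 3 and 8 contrasts change from baseline, which can cost much of the power for NSSI

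*Combined protocol and SAP*

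**What the plan says.** Section 9.3.2 sets up Aim 2 as a comparison of strategies starting with CAMS or TAU "on change (decrease) in suicide-related risk behaviors (SI, NSSI, and suicide attempts—the primary outcomes) from baseline to the end of Stage 2". The model is an LMM "fit with SAS PROC MIXED will be used to analyze the longitudinal data", with time, group and group-by-time terms. The primary contrast is the between-group difference in change from baseline.

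Aim 3 adds: "Both primary and secondary longitudinal outcomes outlined above will be examined using an LMM like that described above". Aim 8 lists the self-injury interview (SITBI) beside the SSI as an endpoint (Table 2). Section 9.3.7 gives it the same LMM, with change from baseline to end of Stage 1 and from Stage 2 randomization to end of Stage 2.

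Three statements bear on how far the LMM reaches:

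- Section 9.3.1 says "suicidal ideation is the primary DV due to relatively low rates of suicidal behaviors post-baseline with college students", and calls Aims 2-5 secondary.
- The Aim 2 text describes the visit schedule with "Note that the primary continuous longitudinal outcome is assessed at baseline, mid-Stage 1 (3 weeks", which is singular and refers to a continuous outcome.
- The Aim 1 text recognises count data ("especially when dealing with a mixture of continuous and count outcomes"), but only for a composite whose form is left to the analysis team.

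Logistic regression appears only for the counselor analyses of Aim 7. Power in section 9.2 is given on the SSI scale or as a standardised effect. No rate, dispersion or power is given for NSSI or attempts.

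**The concern.** NSSI counts are usually mostly zeros with a few very large values, and the plan itself expects low rates after baseline. In such data the raw change score carries the full baseline variance into the comparison. When counts fall over time, the baseline variance is much larger than the follow-up variance, so it swamps the treatment difference. A real halving of self-injury could then be reported as no effect. For attempts, a mean difference in change of a rare event is hard to interpret, and normal-theory inference with a handful of events is unreliable. If the LMM is not meant for these two outcomes, they have no prespecified analysis under these aims, and the choice would be made after the data are seen.

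**Working it through.** **1. The plan's own figure.** Inputs from section 9.2: 240 per arm, d = 0.30, two-sided alpha 0.025. Noncentrality = 0.30 × √(240/2) = 3.286 and the critical value is 2.241, so power = Φ(3.286 − 2.241) = Φ(1.045) = 85.2% (85.0% with the noncentral t). The stated 85% reproduces. It applies to a continuous outcome with the SSI standard deviation of 7 and says nothing about NSSI or attempts.

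**2. What the LMM contrast tests.** With complete data and an unstructured covariance, the baseline-to-week-14 group-by-time contrast equals a t-test on individual change. With linear time and random slopes, it is close to a t-test on individual slopes. Adjusting for baseline clinical severity as a main effect does not help, because a time-constant term cancels out of the change.

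**3. One NSSI case by hand.** Assumptions: mean 2 per window at baseline; 1 (control) and 0.5 (treated) at week 14; Poisson counts with a lognormal person effect (log-SD 1) and occasion-level gamma variation (variance 1). Then Var(Y) = m + m²(2e − 1) = m + 4.437m², and Cov(baseline, week 14) = m₀m₁(e − 1) = 1.718m₀m₁.

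- Baseline variance: 2 + 4 × 4.437 = 19.75. Week 14: 5.44 (control), 1.61 (treated). Covariances: 3.44 and 1.72.
- Change variance: 19.75 + 5.44 − 6.87 = 18.31 (control); 19.75 + 1.61 − 3.44 = 17.92 (treated).
- SE = √((18.31 + 17.92)/240) = 0.389; z = 0.5/0.389 = 1.287; power = Φ(1.287 − 2.241) = **17%**.
- Normal-theory baseline adjustment: pooled slope = 2.577/19.75 = 0.1305; residual variances 4.88 and 1.50; SE = √(6.37/240) = 0.163; z = 3.07; power = Φ(0.83) = **about 80%**.

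In this case baseline adjustment closes most of the gap without a count distribution.

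**4. Simulation.** 500 runs per row, 240 per arm, rate ratio 0.5 at week 14, complete data, no counselor clustering. The comparator is negative binomial (NB) regression of the week-14 count on group and log(1 + baseline count), with robust errors.

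| Control mean, baseline → week 14 | Person log-SD / gamma variance / never-engagers | Change | Slope | NB | NB, size-calibrated |
|---|---|---|---|---|---|
| 2 → 1 | 1 / 1 / 0% | 16% | 21% | 91% | 90% |
| 2 → 1 | 1 / 1 / 40% | 13% | 12% | 76% | 69% |
| 2 → 1 | 1.5 / 1 / 40% | 4% | 7% | 59% | 53% |
| 1 → 0.5 | 1 / 1 / 40% | 10% | 14% | 68% | 64% |
| 0.3 → 0.15 | 1 / 1 / 40% | 8% | 10% | 37% | 26% |
| 2 → 1 | 0.7 / 0.5 / 0% | 42% | 49% | 99% | 99% |
| 1 → 1 | 1 / 1 / 0% | 49% | 67% | 92% | 92% |
| 1 → 1 | 0.7 / 0.5 / 0% | 82% | 91% | 99% | 99% |

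The robust NB test rejected in 2.8-4.8% of null runs against a nominal 2.5%, hence the calibrated column. With model-based errors, its type I error reached 13% under heavy tails.

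A separate simulation under its own assumed rates gave 9-28% (change) against 37-98% (NB) for falling counts, and 52-69% against 86-94% for a stable mean. There, a Gaussian ANCOVA with robust errors did about as well as the NB model (for example 90% against 89%).

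**5. Attempts.** Risk halved, 240 per arm, same alpha, control risks assumed. Expected events are 240 × risk.

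| Control vs treated risk | Expected events | Gaussian, post-baseline | Logistic |
|---|---|---|---|
| 2% vs 1% | 4.8 vs 2.4 | 7% | 12% |
| 5% vs 2.5% | 12 vs 6 | 20% | 22% |
| 10% vs 5% | 24 vs 12 | 44% | 45% |

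A 0/1 change score from a baseline risk of 5-20% has about 2-37% power, against 9-44% for a post-baseline comparison of two proportions.

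**The case against.** The strongest reply is that the plan never says outright that NSSI and attempts go into PROC MIXED. The LMM paragraph speaks of a continuous outcome in the singular, and section 9.3.1 makes ideation the primary dependent variable precisely because behaviours are rare. Aim 3's reference to the outcomes above could point back to that same continuous outcome and the secondary scales. This stands as an ambiguity, and Aim 3 is the firmer text. It does not rescue the plan, because the narrow reading leaves both outcomes with no model.

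A reader might go further and infer that the plan loses most of its power for both behaviours because it assumes normality. The documents do not support that:

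- They give no NSSI or attempt rate for this population, so no single loss can be derived. With a stable, mildly skewed mean the LMM contrast keeps most of its power (82-91% against 99%).
- Normality is not the main cause for NSSI. Gaussian ANCOVA reached 39-99% against 69-99% for a model-based NB whose type I error was inflated.
- For attempts, a logistic model adds 1-2 points at 5-10% risk and 5 points at 2%. Few events limit every method.

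It is also fair that the consequence is bounded: Aims 2 and 3 are secondary, Aim 8 is exploratory, and a composite is planned, although its form is open.

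**Conclusion.** The point holds in this form. Aims 2, 3 and 8 include NSSI and attempts among their outcomes, and the only analysis offered is an LMM on change from baseline. For NSSI, under assumed rates and a halved rate at 240 per arm, that contrast has about 9-28% power against 37-98% when counts fall (4-49% against 37-99% across the tabulated cases), and about 52-69% against 86-94% when the mean is stable. Most of the loss comes from the change score and goes away with baseline adjustment. For attempts, the gain from a binary analysis is an interpretable effect and valid inference with few events, not power.

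These figures assume complete data, no counselor clustering and a single week-14 comparison; a full count mixed model was not simulated. The SSI analysis is not affected.

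**What to change.** - **SSI:** keep the LMM, and state that it applies to SSI as the primary dependent variable and to the continuous secondary scales.
- **NSSI:** prespecify a negative binomial model with log(1 + baseline count) as covariate (the plain log is undefined at zero), log recall-window length as offset, and robust standard errors. The offset is needed because section 5.4 uses one-month windows at all assessments and a three-month window at follow-up. Keep the counselor term. Check type I error by simulation before unblinding, and give Gaussian ANCOVA with robust errors as a sensitivity analysis.
- **Attempts:** analyse any versus none by week 14 and by week 26, with logistic or exact methods.
- **Section 9.2:** say that the power figures on the SSI scale do not apply to NSSI or attempts, and give assumed rates and power for both, or state that they are supportive only.

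The cost is SAP wording and a second procedure (PROC GLIMMIX) in the same software. Effects for these outcomes would be reported as rate or odds ratios, on a different scale from SSI. No new data or participants are needed.
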